10.2. Interim analyses

There will not be a statistical stopping rule. Every three months, the data collected will be analyzed and a record of the monitoring activities will be maintained by the study team.

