2.6. Study Design

- Single Group
- There will be one intervention arm
- The study will be open: no masking is used
- The study is not randomized

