3.5. Study Timeline

3.5.1. Primary Completion:

The study will reach primary completion 36 months from the time the study opens to accrual.

3.6. Study Completion:

The study will reach study completion 36 months from the time the study opens to accrual.

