10.4. Primary Analysis

The primary analysis will be a comparison of tissue stiffness measured by the sound

velocity between malignant and benign nodules. To this end, the two-sided two sample Wilcoxon rank sum test will be used and the statistical significance level is 0.05.

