10.7. Accrual estimates

We expect to accrue 53 patients over 3 years.

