10.8. Criteria for future studies

If current study yields promising results, a larger study may be performed with utilization of other types of ultrasound elastography measurements. Since elastography measurements may vary between ultrasound machines as well as different elastography techniques, it will be important to understand which technique yields the most reliable and consistent results.

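### Do the quarterly analyses in section 10.2, with no stopping rule and no alpha adjustment, undermine the primary test at 0.05?

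*Combined protocol and SAP*

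**What the plan says.** Section 10.2 of the combined protocol and SAP, headed as interim analyses, has two sentences. The first is "There will not be a statistical stopping rule". The second is "Every three months, the data collected will be analyzed and a record of the monitoring activities will be maintained by the study team". It does not define what is analysed, who does it, or what could follow from it.

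The rest of the plan frames these sentences:

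- Section 10.4 gives one primary comparison, velocity in malignant against benign nodules: "the two-sided two sample Wilcoxon rank sum test will be used and the statistical significance level is 0.05".
- Section 10.4.1 gives the analysis population as 53 patients, expected to be 10 with cancer and 43 without. Section 10.6 gives the sample size as 53.
- Section 10.7 says "We expect to accrue 53 patients over 3 years", and section 3.5 says "The study will reach primary completion 36 months from the time the study opens to accrual".
- Section 8.3 has the Protocol Director periodically assess data quality, timeliness, recruitment, accrual and risk against benefit.
- Section 10.8 looks ahead: "If current study yields promising results, a larger study may be performed".

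No section gives an adjusted significance level, a boundary or an alpha-spending function. None says outright that accrual continues to 53 whatever the quarterly data show.

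**The concern.** An interim-analysis section that calls for analysis every three months, with no boundary, beside a primary test at the full 0.05, reads like uncorrected repeated testing. The outcome data are few: velocity and pathology, with no secondary outcome. A reader may therefore suppose that the malignant-benign comparison itself is what gets run each quarter. The absence of a stopping rule removes a boundary, but it does not literally bind the team to a fixed end. Section 10.7 states accrual as an expectation, and section 10.8 sets no criterion for a promising result.

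At stake is the meaning of the final p-value. If the team tested each quarter and stopped, or claimed a result, at the first p below 0.05, the false-positive rate would be well above the stated 5%. A related worry is that, with section 2.6 stating "The study will be open: no masking is used", those taking measurements could learn the emerging pattern while still scanning patients.

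**Working it through.** **Inputs.** 53 patients, 10 malignant and 43 benign (10.1, 10.4.1); difference 0.84 m/sec, SD 0.79 m/sec, power 80% (10.1); two-sided Wilcoxon rank sum test at 0.05 (10.4); accrual over 36 months (3.5, 10.7); analysis every 3 months (10.2).

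**1. The plan's own power figure.** The standardised difference is 0.84 / 0.79 = 1.063. A large-sample check uses the noncentrality 0.84 / (0.79 × √(1/10 + 1/43)) = 3.03. Multiplying by √(3/π) for the Wilcoxon test gives 2.96, and Φ(2.96 − 1.96) = 84%. Simulation with the exact Wilcoxon p-value (Gaussian data, 200,000 replicates) gives 81.5%. The stated 80% is reproduced, for one final test.

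**2. Number of looks.** 36 / 3 = 12 quarterly points. The last coincides with the end, so 11 are interim. With even accrual they fall at n = 4, 9, 13, 18, 22, 26, 31, 35, 40, 44, 49 and 53. The expected number of malignant nodules is 4 × 10/53 = 0.75 at the first look and 26 × 10/53 = 4.9 at the sixth.

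**3. Size when the plan is followed as written.** The test is run on all 53 patients and the looks change nothing. The null distribution of the final rank sum then does not depend on how often the data were viewed. Summing the exact null distribution for 10 against 43 over the values with two-sided p ≤ 0.05 gives 4.8%. In the null simulation (15,000 replicates) the final test rejected in 4.6% of trials with 1, 4 or 12 looks, which agrees with 4.8% within Monte Carlo error.

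**4. Size if every look were a test that could be claimed.** Two steps are added that the plan does not contain: testing by malignancy status at each look at 0.05, and claiming the first significant result.

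| Scenario | False-positive rate |
|---|---|
| One final test, exact size | 4.8% |
| 4 looks, exact Wilcoxon | 10.9% |
| 12 looks, exact Wilcoxon, 10 malignant in random order | 14.9% |
| 12 looks, exact Wilcoxon, random number malignant | 14.9% |
| 12 looks, large-sample normal | 20.7% |

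A separate simulation with the normal approximation to the Wilcoxon test gives 14.0% for 12 looks with continuity correction, 16.6% without, and 10.8% if testing starts only at 5 malignant nodules. The 12-look exact figures carry a Monte Carlo standard error of about 0.3 points.

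**5. What an alpha adjustment would cost.** Holding 0.05 over 12 looks needs a constant level of about 0.015 per look, or an O'Brien-Fleming-type boundary with a final level of about 0.036. The final test alone would then have 66% or 77% power, against 81.5% at 0.05. The plan provides for no early claim, so that power would be given up for nothing.

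**The case for a change.** The strongest opposing case is that the wording does not secure the harmless reading. Oversight already has its own place in section 8.3, whereas section 10.2 sits in the statistical chapter under an interim-analysis heading. There is little to analyse besides velocity against pathology, since section 7.2 expects no adverse events. Section 10.3 provides summaries by malignancy status without reserving them for the end. A team could compare the groups each quarter, or react to a favourable look, without plainly breaching any sentence.

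Part of this stands. The scope of the quarterly analysis is undefined, and no explicit commitment to continue is written. But the same sentence in section 10.2 calls the work monitoring, which fits the periodic assessments in section 8.3. The natural reading of having no statistical stopping rule, beside a fixed 53 patients and one primary test, is that the looks do not end the study. Section 10.8 ties a larger study to the results of this one and does not mention interim results. Stopping or claiming early would have to be added to the plan; nothing in it provides for either.

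The measurement-bias argument is weaker still. Section 10.2 assigns only the record to the study team, and no section says who scans or who analyses. Section 9.2 has the machine calculate the velocity, and no section says that the measurement depends on the operator. On masking the documents disagree: section 2.6 says there is none, while section 10.1 calls the study blinded. Elastography comes before the biopsy or resection (4.1, 10.1), so the result of that procedure is not yet known when velocity is taken.

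**Conclusion.** The concern does not call for a change. Followed as written, with 53 patients and one final two-sided Wilcoxon test, the type I error is 4.8%, and viewing the data each quarter does not move it. The rise to about 15% (about 11% to 21% across the assumptions tried) is conditional on testing the primary comparison every quarter and claiming the first p below 0.05, which the plan does not describe. That range should not be read as a property of this design.

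The remaining gap is one of detail: what the quarterly review covers, and an explicit statement that accrual does not depend on it. In a small single-arm imaging study with no treatment, analysts would take the review as monitoring and run the confirmatory test once at the end. Spelling that out would change no planned result.

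This rests on the final test being the only confirmatory one and on no look altering accrual. The simulated figures also assume even accrual, one nodule per patient, and pathology known at each look.

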10.3. Descriptive Statistics and Exploratory Data Analysis

The distribution of the elastography measurements will be summarized by mean and standard deviation. If the distribution is highly non-Gaussian, then median and other quantiles will be provided as well. The summaries will be provided by malignancy status.

10.4. Primary Analysis

The primary analysis will be a comparison of tissue stiffness measured by the sound

velocity between malignant and benign nodules. To this end, the two-sided two sample Wilcoxon rank sum test will be used and the statistical significance level is 0.05.

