1. OBJECTIVES

1.1. Primary Objective

The purpose of this study is to determine the utility of ultrasound elastography in evaluation of thyroid nodules. Elastography is a non-invasive method in which stiffness or strain images of soft tissues are used to characterize a nodule or mass lesions. Tissue that is more stiff is thought to have a greater risk of malignancy.

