2.4. Rationale

Thyroid nodules are extremely common, affecting nearly half of the adult population. Although extremely common, a minority, between 1.5 – 10% of thyroid nodules, are malignant. [1] Differentiation between benign and malignant nodules however, based on physical examination and ultrasound imaging is very difficult and generally is referred for invasive percutaneous biopsy or surgical excision for definitive diagnosis.

Because of the very common occurrence of thyroid nodules in the general public, there is a great need for a noninvasive means of stratifying those who are at greater risk of malignancy from those who are more likely to harbor a benign nodule for which no treatment is necessary.

Recent studies have examined elastography in thyroid nodules with findings of high sensitivity and good specificity. [2] Other investigators have looked at elastography in evaluation of other [3] [4] It is thought that lesions that are stiffer are more likely to represent malignancy or other pathology than benign or normal tissue which tend to be more softer.

Elastography is a noninvasive ultrasound technology which can evaluate the stiffness of a lesion compared to the background tissue. There are two major methods of measuring stiffness: strain imaging, and shear wave velocity measurement. In strain imaging, ultrasound maps the relative tissue deformity by extrinsic compression and provides a color map. Greater deformation with pressure corresponds to more elastic tissue and less deformation corresponds to stiffer tissue. In the second method, shear waves are sent through a given volume of tissue and the speed of the shear wave propagation is measured. Since stiffer tissues have higher shear wave velocities, this can be correlated with tissue

stiffness to provide a more quantitative measurement. Velocities can then be used to calculate Young modulus in kPa. [5]

Most shear wave elastography measurements currently available use a single point measurement; however, a new 2-D shear wave elastography measurement technique will be used in our study to measure stiffness of thyroid nodules. This will allow sampling of a larger area of a nodule instead of just one point, which may be more representative of the nodule's overall stiffness.

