9. MEASUREMENTS

9.1. Primary and Secondary Outcome measures

Elastography shear wave velocity measurements of thyroid nodules will be compared to fine needle aspiration biopsy results or surgical pathologic specimens, if available. No secondary outcome measurements will be made.

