9.5. Secondary Outcome

There is no secondary outcome.

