10. STATISTICAL CONSIDERATIONS

10.1. Statistical Design

This is a prospective single arm blinded study in which patients who come for biopsy or surgical resection will be analyzed with elastography prior to biopsy or surgical resection. A sample size of 10 vs 43 provide 80% power for detecting a difference of 0.84 m/sec at the significance level of 0.05 based on Wilcoxon rank sum test assuming that the sound velocity for benign (and malignant nodules) follows a Gaussian distribution). The standard deviation is 0.79 meters/second based on the observed standard deviation from our pilot data.

We propose to use Wilcoxon rank sum test for its robustness in cases where the velocity does not follow the Gaussian distribution. Even if the Gaussian assumption is true, the Wilcoxon rank sum test is almost as powerful as the parametric t-test.

Randomization

Patients are not randomized in this study.

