10.4.1. Analysis Population

Analysis population is 53 patients expected to consist of 10 cancer patients and 43 non-cancer patients.

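### The objective is the utility of elastography, but the plan yields only a rank-sum p-value and group summaries, with no measure of discrimination and no confidence interval

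*Combined protocol and SAP*

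**What the plan says.** Section 1.1 gives the single objective: "The purpose of this study is to determine the utility of ultrasound elastography in evaluation of thyroid nodules". Section 2.4 explains why it matters: "there is a great need for a noninvasive means of stratifying those who are at greater risk of malignancy". Section 9.1 defines the outcome: "Elastography shear wave velocity measurements of thyroid nodules will be compared to fine needle aspiration biopsy results or surgical pathologic specimens, if available".

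For the analysis, Section 10.4 says: "To this end, the two-sided two sample Wilcoxon rank sum test will be used and the statistical significance level is 0.05". Section 10.4.2 repeats the test and adds unspecified summary statistics for velocity by malignancy status. Section 10.3 plans means and SDs, with the median and other quantiles if the distribution is far from Gaussian: "The summaries will be provided by malignancy status". Section 10.4.1 sets the expected numbers: "Analysis population is 53 patients expected to consist of 10 cancer patients and 43 non-cancer patients".

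Nothing else is planned. Section 9.5 states: "There is no secondary outcome". Section 1.2 has no secondary objective, and Section 10.5 marks the secondary analysis as not applicable. ROC, PPV, NPV and CI appear in the list of abbreviations and in no planned analysis.

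**The concern.** Sorting nodules by malignancy risk is a discrimination question: how well does velocity separate malignant from benign nodules, and how precisely is that known? A rank-sum p-value answers a narrower question, whether there is any tendency for one group to be higher. Followed exactly, the plan produces a p-value and descriptions of each group, and neither estimates separation.

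With about 10 cancers, precision matters as much as significance. Section 10.8 makes a larger study depend on promising results, and a p-value alone is a poor basis for that decision.

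A reader could rebuild a mean difference and its CI from the planned means, SDs and counts. Rebuilding discrimination from them requires a Gaussian shape, and Section 10.1 chose the test so as not to depend on that: "We propose to use Wilcoxon rank sum test for its robustness in cases where the velocity does not follow the Gaussian distribution".

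**Working it through.** **Inputs.** Difference 0.84 m/s, SD 0.79 m/s, 10 vs 43, two-sided 0.05, power 80% (Sections 10.1, 10.4 and 10.4.1). Assumed: the same SD in both groups, Gaussian velocities, one nodule per patient, no losses.

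**1. The plan's own figure.** Simulating the rank-sum test with its exact critical values (reject if U ≤ 128 or U ≥ 302; 100,000 data sets) gives 81.4% power. The stated 80% reproduces, and the sample size is not in dispute.

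**2. AUC implied by the design.**
- d = 0.84 / 0.79 = 1.063
- AUC = Φ(d/√2) = Φ(0.752) = 0.774

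**3. Its precision at 10 vs 43.** Let A be the AUC. Let Q be the probability that two malignant nodules both exceed one benign nodule; under this model it equals the probability that one malignant nodule exceeds two benign ones. Q = 0.652.
- SE = √{[A(1−A) + 9(Q−A²) + 42(Q−A²)] / 430} = 0.082
- On the logit scale: ln(0.774/0.226) = 1.231, with SE 0.0817 / (0.774 × 0.226) = 0.467
- 1.231 ± 1.96 × 0.467, transformed back: **0.58 to 0.90**

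The Hanley-McNeil formula gives SE 0.092 and a logit interval of 0.55 to 0.91. The choice of formula moves the limits slightly; the interval is wide either way.

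**4. Smallest significant result.** The exact two-sided p is 0.048 at U = 302 and 0.051 at U = 301. The boundary AUC is 302/430 = 0.702. The method of step 3 gives a 95% CI of about **0.50 to 0.85**.

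**5. Non-significant results.** If the design difference is true, about 73% of non-significant trials have an upper AUC limit of 0.80 or more (repeat simulations gave 72% to 75%). This depends on the true AUC: it falls to 54% at 0.70, 27% at 0.60 and 8% at 0.50.

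**6. Fewer cancers.** Section 2.4 puts malignancy at up to 10% of nodules; 10% of 53 is about 5. At 5 vs 48 the SE is 0.109 and the CI is **0.50 to 0.92**. A cohort referred for biopsy may have a higher rate.

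**7. What the planned summaries already give.**
- Mean difference: 0.84 ± 2.008 × 0.79 × √(1/10 + 1/43) = 0.84 ± 0.56, or 0.28 to 1.40 m/s.
- AUC rebuilt as Φ[(mean₁ − mean₀)/√(SD₁² + SD₀²)]: for log-normal velocities (assumed) with a true AUC of 0.774, the result is 0.748 at log-SD 0.5 and 0.725 at log-SD 0.7. At log-SD 0.2 to 0.3 it is 0.770 to 0.764, a negligible error.

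**8. Behaviour of the proposed interval** (DeLong variance, logit scale; 40,000 runs at 10 vs 43, AUC 0.774). Coverage is 94.2%, against 90.3% without the logit. The test is significant while the CI includes 0.5 in 5.5% of trials, and the reverse occurs in 1.4%, so the two disagree in about 7%.

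**The case against.** The strongest reply is that Section 1.1, read in full, is an association hypothesis. It ends by saying that stiffer tissue is thought to carry more malignancy risk. Section 2.5 reports higher values in malignant nodules, and Section 9.1 compares velocity with pathology. The test matches that outcome, and a group comparison is a conventional first step in a 53-patient study that Section 10.8 treats as a prelude to a larger one. On this reading only the word utility is loose. Moreover, the AUC is a rescaling of the planned test statistic, the summary statistics in Section 10.4.2 are left open, and the AUC is not clinical utility either.

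Part of this stands. The test is valid and should stay. Rewording Section 1.1 would be a legitimate cure. The error from rebuilding an AUC out of means and SDs is modest, 0.03 to 0.05 in the skewed examples, against an interval about 0.32 wide; strong skew would also trigger the quantiles in Section 10.3.

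The rest does not remove the gap. The open-ended summaries describe velocity within each group, which is not discrimination, and no interval is promised. That U can be rescaled makes the fix easy but commits nobody to reporting it. The small, early nature of the study makes an interval more useful.

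**Conclusion.** The concern holds. The plan's test is sound and adequately powered for the assumed difference, but as written the study will not estimate what its objective asks. At the design difference the AUC would be 0.77, known only to within about 0.58 to 0.90. The weakest significant result is an AUC of 0.70 with an interval starting at about 0.50.

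These figures illustrate the plan's own alternative and do not forecast performance. They rest on equal Gaussian SDs, one nodule per patient and the expected 10/43 split; fewer cancers would widen the intervals. No stated number, sample size or significance level is wrong. This is a change that should be made; it is not a flaw that invalidates the primary analysis.

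**What to change.** Add to Sections 10.4 and 10.4.2:

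> The effect estimate is the AUC, U/(n_malignant × n_benign), using the observed group counts and one nodule per patient, with a 95% CI from the DeLong variance on the logit scale, or a Newcombe score-type interval if the observed AUC is 0 or 1. If several nodules per patient are analysed, the test and the CI both use a variance clustered by patient. The two-sided Wilcoxon rank sum test at 0.05 remains the primary test and governs the significance statement; the CI describes precision. Any sensitivity or specificity at a cut-off chosen from these data is exploratory and is given with exact 95% CIs.

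If only association is intended, narrow the wording of Section 1.1 instead.

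**Cost.** A few sentences and a few lines of code; no new patients, data or alpha. The interval will be visibly wide. It will disagree with the test about 0.5 in roughly 7% of trials at the design difference, which is why the text says which one governs. Coverage is approximate: about 90% with 5 malignant nodules, and 88% to 95% if malignant velocities have twice the SD of benign ones. If some or all patients contribute two nodules and this is ignored, coverage falls to 88% to 93% (within-patient correlation 0.3 to 0.6, assumed), hence the clustering clause. The AUC measures discrimination and does not capture clinical utility in full.

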10.4.1. Analysis Population

Analysis population is 53 patients expected to consist of 10 cancer patients and 43 non-cancer patients.

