5.2 Alternatives

Alternative is to not participate in the study and continue with planned standard of care ultrasound and/or fine needle aspiration of thyroid nodule.

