9.2. Measurement methods

Elastography shear wave velocity measurements of thyroid nodules (which are calculated by the ultrasound machine at the time of the elastography measurements) will be compared to fine needle aspiration biopsy results or surgical pathologic specimens, if applicable.

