9.3. Measurement Time Points

Elastography shear wave velocity measurements of thyroid nodules will be compared to fine needle aspiration biopsy results or surgical pathologic specimens, if applicable. No follow-up imaging or assessment will be required.

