10.4.2. Analysis Plan

Appropriate summary statistics will be provided for the sound velocity by the malignancy status. two-sided two sample Wilcoxon rank sum test will be used to compare of tissue stiffness measured by the sound velocity between malignant and benign nodules

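### Do sections 10.4.1 and 10.4 treat a nodule without a definitive pathology result in two different ways?

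*Combined protocol and SAP*

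**What the plan says.** Section 10.4.1 reads "Analysis population is 53 patients expected to consist of 10 cancer patients and 43 non-cancer patients". Section 10.6 gives 53 as the sample size, and section 10.7 adds "We expect to accrue 53 patients over 3 years". The primary test in section 10.4 compares the "velocity between malignant and benign nodules", and section 10.4.2 repeats this as a comparison of "tissue stiffness measured by the sound velocity between malignant and benign nodules". Section 10.1 bases its power statement on 10 versus 43, with velocity distributions for benign and malignant nodules.

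For the reference result, section 9.1 says that velocities are "compared to fine needle aspiration biopsy results or surgical pathologic specimens, if available". Section 9.2 says "compared to fine needle aspiration biopsy results or surgical pathologic specimens, if applicable". Section 9.3 repeats that and adds "No follow-up imaging or assessment will be required". Sections 3.1.2, 4.1 and 10.1 limit the study to nodules that can be aspirated, in patients already coming for biopsy or resection.

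No section mentions a non-diagnostic, indeterminate or missing result, or says whether aspiration or surgery prevails if they disagree.

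**The concern.** The same number, 53, serves as accrual, sample size and analysis population, so the plan appears to place every enrolled patient in one of two groups. Non-cancer can be read to include any nodule not shown to be cancer, whereas benign cannot. On that reading an unclear aspirate is inside the analysis set of section 10.4.1 and outside the test of section 10.4.

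Two things could be at stake. One is power: only 10 cancers are expected, so each one lost or misplaced matters. The other is the 5% level: if the handling is open and the data are visible, the more favourable handling could be chosen. Section 2.6 says there is no masking, section 10.1 calls the study blinded, and section 10.2 has the data analysed every three months.

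**Working it through.** **Inputs.** Difference 0.84 m/s, SD 0.79 m/s and 10 versus 43 come from section 10.1. The two-sided Wilcoxon rank sum test at 0.05 comes from section 10.4. The number of unclassified nodules is not in the documents; 1, 2, 5, 8 and 10 of 53 are assumptions.

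**Step 1: do the sections conflict?** Section 10.4.1 gives 10 + 43 = 53 as what is expected. It does not assign unclear results to a group. Section 10.4 names the two groups and states no exclusion. Section 10.1 powers the same 10 and 43 as malignant and benign. The two pairs of labels therefore name the same groups, and an unclear result is addressed in neither section.

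**Step 2: the plan's own power.** A first approximation is Φ(δ / (σ√(1/n₁ + 1/n₂)) − 1.96).

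- √(1/10 + 1/43) = 0.351, and 0.84 / (0.79 × 0.351) = 3.03. Then Φ(3.03 − 1.96) = Φ(1.07), about 85.7%, for a comparison of means.
- With the Wilcoxon efficiency factor 3/π: 3.03 × √0.955 = 2.96, and Φ(1.00) is about 84.1%.
- Direct simulation of the planned test with Gaussian data gives 81.3% (normal-approximation p-value, 40,000 runs) and 81.5% (exact p-value, 100,000 runs).

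The stated 80% is reproduced.

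**Step 3: one unclassified nodule (exact test).**

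| Handling | Groups | Power |
|---|---|---|
| Benign nodule left out | 10 vs 42 | 81.5% |
| Cancer left out | 9 vs 43 | 78.1% |
| Same cancer counted as non-cancer | 9 vs 44 | 76.6% |

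**Step 4: more unclassified nodules, lost in proportion (normal approximation).** With 5 lost, 10 × 48/53 = 9.1, giving 9 vs 39. With 8 lost, 10 × 45/53 = 8.5; the run used 8 vs 37. With 10 lost, 10 × 43/53 = 8.1, giving 8 vs 35. The last two columns count the nodules as non-cancer, with an assumed share of them malignant.

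| Unclassified | Left out | Non-cancer, 19% malignant | Non-cancer, 40% malignant |
|---|---|---|---|
| 5 | 76.4% | 75.9% | 73.2% |
| 8 | 72.0% | 70.4% | 66.1% |
| 10 | 71.4% | 69.1% | 64.4% |

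In each of these cases, leaving the nodules out has at least as much power as counting them as non-cancer.

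**Step 5: the 5% level.** With no true difference, a single fixed handling gives 4.7% to 5.0%. Keeping the smaller p-value of the two handlings (left out, or non-cancer) gives 5.1%, 5.4% and 5.7% with 1, 2 and 5 unclassified nodules. The excess over 5% is 0.1, 0.4 and 0.7 percentage points.

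**The case for a change.** The best case for a change is that the study has one outcome and one test, and pathology alone forms the two groups. A short sentence on unclassified nodules, with surgical pathology taking precedence, would need no extra patients and would leave nothing to judgement. Participation ends with the scan (section 5.1), so the study itself resolves no unclear result. If counting unclear nodules as malignant were also open, the smallest-p rates would be 6.4%, 7.1% and 8.2%. Sorting five of them by velocity would give 9.5%.

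The omission stands. The larger error rates do not carry it, because nothing in the text supports counting an unclear nodule as malignant or sorting by velocity, and all the rates assume deliberate selection. Section 10.2 calls for three-monthly analysis and a monitoring record; it does not say that the groups are tested each time.

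Some of the supporting text is also weaker than it looks. The phrase "continue with planned standard of care ultrasound and/or fine needle aspiration of thyroid nodule" in section 5.2 describes people who do not take part. The conditional wording in sections 9.1 to 9.3 most naturally qualifies surgical specimens, since not every patient has surgery.

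The power loss with several unclassified nodules is real, but it depends on how many results are definitive. A handling rule would not recover it, and the documents give no rate from which to enlarge accrual.

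Two wording mismatches are genuine: no masking (2.6) against blinded (10.1), and Appendix A item 2, which drops the aspiration condition of 3.1.2. The machine calculates velocity at the scan, before biopsy or resection, and patients are already coming for one or the other. Neither mismatch is shown to alter a result.

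**Conclusion.** Sections 10.4.1 and 10.4 do not contradict each other. The plan leaves a detail unstated, and an analyst would fill it sensibly: a test of malignant against benign nodules uses those with a definitive result, and the rest are counted and described. The 80% is right for 10 versus 43 classified nodules. Leaving out one cancer takes the simulated 81.5% to about 78%; five or ten nodules lost in proportion would take it to about 76–77% or 71–72%. Those losses rest on assumed counts. Between the two handlings that the wording could bear, the inflation of the 5% level is at most about 0.7 points, and only with deliberate selection and five unclassified nodules. The mismatches on masking and in Appendix A are clerical. No change to the plan follows.
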